1. INTRODUCTION

HMI-115 is a highly specific human monoclonal antibody that will be investigated for safety and efficacy in pre-menopausal women with moderate to severe endometriosis associated pain.

A First in-human (FiH) study with HMI-115 has already established the safety and tolerability of HMI-115 when administered subcutaneously in post-menopausal women aged between 45 to 65 years in single doses up to 240 mg and multiple doses up to 90 mg once every 2 weeks (Q2W) for 6 weeks. This study aims to evaluate the safety and efficacy of HMI-115 versus a placebo in pre-menopausal women aged 18 to 49 years diagnosed with moderate to severe endometriosis associated pain.

The analyses described in this Statistical Analysis Plan (SAP) are based upon the following study documents:

- Study Protocol Version 6.1 (19 Sep 2024)
- Electronic Case Report Form (eCRF), Version 6.0 (12 Dec 2023)

Data will be summarized and listed according to the SAP. The details will be reflected in the document of Table, Listing, and Figure Shells.

The planned analyses identified in this SAP may be included in clinical study reports (CSRs), regulatory submissions, or future manuscripts. Also, post hoc exploratory analyses not necessarily identified in this SAP may be performed to further examine study data. Any post hoc, or unplanned, exploratory analyses performed will be clearly identified as such in the final CSR.

In addition, the SAP V1.3_special version for research paper publication is generated for the requirement of research paper publication only. Compared to the SAP V1.3, the change is that the SAF will be same as the PAS for all safety analysis.

PROJECT OVERVIEW

[figure not shown]
1.1 Study Design

This is a Phase 2, multicenter, double-blind, placebo-controlled, randomized study to assess the safety and efficacy of HMI-115 subcutaneously administered monoclonal antibody versus placebo in pre-menopausal women with moderate to severe endometriosis-associated pain. The planned study regions include China, the United States of America (USA) and European countries.

The study will comprise of three periods:

1. Screening Period of up to 75 days prior to first dose
 - Screening Visit 1
 - Screening Visit 2 (at least 35 days before Visit 3 to ensure at least 5 weeks baseline pain score obtained before randomization)
2. Treatment Period (12 weeks). Subjects will be given subcutaneous (s.c.) injections Q2W (once every 2 weeks).
3. Follow-up Period of 12 weeks.

Figure 1: Study Design of the Study

IMP: investigational medicinal product.

Eligible subjects will be randomized into four arms: placebo, 60 mg, 120 mg, and 240 mg HMI-115 in a 1:1:1:1 ratio with 38 subjects/arm. The randomization will be stratified with two stratification factors 1) region and 2) participation in the intensive Pharmacokinetics(PK) sampling subset.

A subject is considered to have completed the study if she has completed all phases of the study including the last scheduled procedure (follow-up at Week 25 for safety and to cover 5 half-lives) as shown in the Schedule of Activities (SoA) (Section 1.3 of Protocol).

The end of this clinical study is defined as the date of the last visit of the last subject in the study or last scheduled procedure shown in the SoA (Section 1.3 of Protocol) for the last subject in the study globally.

1.2 Objectives

1.2.1 Primary objective(s)

The primary objective is to study the efficacy of HMI-115 for 12 weeks compared with placebo in the management of endometriosis-associated pain based on subjects with surgical diagnosis.

1.2.2 Secondary objective(s)

The secondary objective is to study the safety, tolerability, and persistence of efficacy of HMI-115 compared with placebo.

1.2.3 Exploratory objective(s)

The exploratory objective is to explore the effect of HMI-115 on Quality of life, PK, PK-PD (Pharmacodynamics) relationship, and immunogenicity.

1.3 Endpoints

1.3.1 Efficacy endpoint(s)

All subjects will be administered an e-Diary after adequate training at Visit 2. Subjects are required to record uterine bleeding and endometriosis-associated pain every day at around the same time for the entire duration of the study. The use of rescue medications for endometriosis-associated pain will also be recorded.

Numeric Rating Scale (NRS) for pain will be used to measure Dysmenorrhea (DYS) from Baseline to Week 12 and Baseline to Week 24 with pain scale ranging from 0 (no pain) to 10 (severe pain). Non-menstrual pelvic pain (NMPP) and dyspareunia (DYSP) will be also measured using the NRS pain scale from Baseline to Week 12, and Week 24.

Endometriosis Daily Impact Pain Scale will be used to record the mean change every month from Baseline to Week 12 and 24 with the pain scale ranging from 0 (no pain) to 3 (severe pain).

1.3.1.1 Primary Efficacy Variable

- Change in DYS measured by NRS from Baseline to Week 12 measurement

1.3.1.2 Secondary Efficacy Variable

- Change in DYS measured by NRS from Baseline to Week 24 measurement
- Change in NMPP measured by NRS from Baseline to Week 12 measurement and Week 24 measurement
- Change in DYSP measured by NRS from Baseline to Week 12 measurement and Week 24 measurement
- Change from Baseline (CFB) in the monthly mean Endometriosis Daily Impact Pain Scale for DYS, NMPP and DYSP at Week 12 measurement and 24 measurement
- CFB by visit in permitted rescue medication use
- Change in menstrual period heaviness (bleeding) from Baseline by visit

1.3.2 Safety and Tolerability endpoints(s)

1.3.2.1 Adverse Events (AEs)

All AEs will be collected from the signing of informed consent form (ICF) until the end of study participation at the time points specified in the SoA (Section 1.3 of Protocol).

1.3.2.2 Vital Signs

The following vital signs will be measured:

- Blood pressure (systolic and diastolic [mmHg])
- Pulse (beats/min)

- Tympanic body temperature (°C)
- Respiratory rate (breaths/min)

1.3.2.3 **Physical Examinations**

A complete physical examination will include, at a minimum, assessments of General appearance, head, eyes, ears, nose, throat (HEENT), Neck (including thyroid), Lung/pulmonary, Chest (including breast), Cardiovascular, Abdomen, Back, Neurological, Extremities, Skin and Lymph nodes. A brief physical examination will include, at a minimum, assessments of General appearance, HEENT, Neck, Lung/pulmonary, Breast, Cardiovascular, Abdomen, Extremities and Skin.

The time points examinations are shown in the SoA (Section 1.3 of Protocol). Height (cm) and weight (kg) will also be measured and recorded at specified period.

1.3.2.4 **Concomitant Medication**

Concomitant medications will be recorded until last study visit.

1.3.2.5 **Twelve-Lead Electrocardiogram (ECG)**

The following 12-Lead ECG parameters will be collected:

- HR (beats/min)
- PR interval (msec)
- QRS interval (msec)
- QT interval (msec)
- QT interval corrected for heart rate (QTc) (msec) (QTcB and QTcF)

1.3.2.6 **Clinical Laboratory Tests**

Clinical laboratory tests include hematology, coagulation, clinical chemistry, urinalysis, hormones and CA-125. All tests will be obtained as outlined in the SoA (Section 1.3 of Protocol).

1.3.2.7 **Dual Energy X-ray Absorptiometry (DXA) Scan**

DXA scan results contain the lumbar spine, total hip, and femoral neck. The blinded reads of scans and management will be made based on the central review or local readings.

Subjects who prematurely discontinue IMP treatment prior to week 11 will not have a DXA at the end of treatment (EOT) visit or in the Post-treatment Follow-up Period. Subjects who become pregnant during the study will not have protocol required DXA scans.

1.3.2.8 **Transvaginal Ultrasound (TVU)**

- Assessments for TVU include, but are not limited to, the following:
- Endometrial thickness (double layer, mm)
- Other endometrial findings such as heterogeneity or other abnormality
- Presence, size and appearance of ovarian cysts or masses
- Presence, location and size of uterine fibroids
- Endometriomas

The Screening TVU may be repeated per protocol (e.g., ovarian cyst criteria) or as clinically appropriate. An unscheduled (elective) TVU may also be performed as clinically indicated for subject evaluation during the course of the study.

1.3.3 **Exploratory endpoints(s)**

1.3.3.1 **Other Patient-Reported Outcomes**

- Quality of Life assessment with health-related quality of life questionnaire (HRQoL) (Endometriosis Health Profile-5 [EHP-5])

The EHP-5 is a HRQoL scoring that has a core questionnaire and modular questionnaire with a 4-point rating scale for each item (0 = never, 1=rarely, 2=sometimes, 3=often, 4 = always). Anything that is not applicable to the subject in the questionnaire will be marked not relevant.

- Response to Patient Global Impression of Change (PGIC)

Subjects will score the PGIC as shown in the SoA (Section 1.3 of Protocol). The PGIC questionnaire is a self-reported 7-point scale rating a subject's overall impression of change in their endometriosis-associated pain since start of IMP, where 1=very much improved, 2=much improved, 3=minimally improved, 4=not changed, 5=minimally worse, 6=much worse, 7=very much worse.

1.3.3.2 **PK**

- AUC_{0-10d} , $AUC_{0-\infty}$, % AUC_{extrap} , C_{max} , T_{max} , λ_z , $t_{1/2}$, MRT, CL/F, and V_z/F following dose 1
- $T_{\text{max ss}}$, $C_{\text{ss trough}}$, $C_{\text{ss max}}$, $C_{\text{ss av}}$, $t_{1/2}$, $AUC_{0-\tau_{\text{ss}}}$, CL/F, V_z/F et al following last dose
- Accumulation ratio (AR) for both C_{max} and AUC

PK concentration data will be obtained at the time point(s) described in the protocol as follows:

Blood samples will be collected to determine PK profile from Day 1 to Day 169. A full PK sampling strategy will be followed for a subgroup of ten subjects per arm conduct at selected sites (refer Table 1-2 in the Protocol). Only sparse sampling will be obtained from the rest of the subjects (refer Table 1-3 in the Protocol).

1.3.3.3 **PK-PD**

Relationship between HMI-115 plasma concentration/exposure and pelvic pain score measured by NRS (cyclic = DYS, non-cyclic = NMPP+DYSP, and average)/side effects will be detected.

1.3.3.4 **Immunogenicity**

- Anti-drug antibody (ADA)
- Neutralizing antibody (NABs).

To assess the overall immunogenicity potential of HMI-115, subject's blood will be tested for anti-drug antibody (ADA) production: ADA (positive/negative and titer) and neutralizing antibodies (NAB) (positive/negative and titer only in subjects with ADA positive result). The time points for ADA determinations in blood are provided in SoA with one additional sampling point at week 17. All samples for ADA should be collected together with the corresponding PK sample.

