A certified central laboratory will be utilized to process and provide results for all blood tests.

DXA will be analyzed/evaluated centrally by an experienced and qualified imaging vendor.

Procedures that allowed to be repeated during screening period are listed in section 10

Version 6.0 17 of 138 April 11,2024

Table 1-2 Intensive PK Subset (N=10 per arm)

WEEK STUDY DAY		TIME (in r	elation to dosing)	TIME WINDOW
		hour	day	
Week 1	Day 1(first dose)	Pre-dose	Pre-dose	
Week 1	Day 3	+48 h (post-first dose)	+2 day (post-first dose)	+/-2 h
Week 1	Day 5	+96 h (post-first dose)	+4 day (post-first dose)	+/-2 h
Week 1	Day 7	+144 h (post-first dose)	+6 day (post-first dose)	+/-6 h
Week 2	Day 11	+240 h (post-first dose)	+10 day (post-first dose)	+/-12 h
Week 3	Day 15±3	Pre-dose	Pre-dose	Within 2 h before dosing
Week 5	Day 29±3	Pre-dose	Pre-dose	Within 2 h before dosing
Week 9	Day 57±3	Pre-dose	Pre-dose	Within 2 h before dosing
Week 11	Day 71±3(last dose)	Pre-dose	Pre-dose	Within 2 h before dosing
Week 11	Day 73	+48 h (Post-last dose)	+2 day (Post-last dose)	+/-2 h
Week 11	Day 75	+96 h (Post-last dose)	+4 day (Post-last dose)	+/-2 h
Week 11	Day 77	+144 h (Post-last dose)	+6 day (Post-last dose)	+/-6 h
Week 12	Day 81	+240 h (Post-last dose)	+10 day (Post-last dose)	+/-1 day
Week 13	Day 85	+336 h (Post-last dose)	+14 day (Post-last dose)	+/-2 days
Week 17	Day 113	+ 1008 h (Post-last dose)	+42 day (Post-last dose)	+/-7 days
Week 19	Day 127	+1344 h (Post-last dose)	+56 day (Post-last dose)	+/-7 days
Week 21	Day 141	+ 1680 h (Post-last dose)	+70 day (Post-last dose)	+/-7 days
Week 25	Day 169	+ 2352 h (Post-last dose)	+98 day (Post-last dose)	+/-7 days

Version 6.0 18 of 138 April 11,2024

Table 1-3 Sparse PK Sampling

WEEK	STUDY DAY	TIME (in relation to dosing)		TIME WINDOW
		hour day		
Week 1	Day 1(first dose)	Pre-dose	Pre-dose	
Week 1	Day 7	+144 h (post-first dose)	+6 (post-first dose)	+/-2 days
Week 3	Day 15±3	Pre-dose	Pre-dose	Within 2 h before dosing
Week 5	Day 29±3	Pre-dose	Pre-dose	Within 2 h before dosing
Week 9	Day 57±3	Pre-dose	Pre-dose	Within 2 h before dosing
Week 11	Day 71±3(last dose)	Pre-dose	Pre-dose	Within 2 h before dosing
Week 11	Day 77	+144 h (post-last dose)	+6 day (post-last dose)	+/-2 days
Week 13	Day 85	+336 h (post-last dose)	+14 day (post-last dose)	+/-4 days
Week 17	Day 113	+ 1008 h (post-last dose)	+42 day (post-last dose)	+/-7 days
Week 25	Day 169	+ 2352 h (Post-last dose)	+98 day (Post-last dose)	+/-7 days

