Pharmacokinetic (PK) evaluation of HMI-115 demonstrated that the drug reached peak plasma concentration approximately 4 to 11 days after administration of 7.5 mg to 240 mg subcutaneously. Following repeated dosing and an accumulation index of approximately 2, a more than dose proportional increase in the main PK parameters was observed. Pharmacodynamic (PD) evaluation of HMI-115 demonstrated no effect on the circadian rhythm of PRL secretion.¹

HMI-115 was well tolerated in FiH studies and animal studies. In post-menopausal women, no specific adverse events (AE) patterns or clinically significant effects on the vital signs, ECG or laboratory parameters were observed. As a fertility and early embryonic study in female

Cynomolgus monkeys demonstrated that weekly administration of HMI-115 at doses up to 50 mg/kg prior to mating, throughout mating and post-mating/early gestation did not affect the mating success and had no influence on pregnancy outcome, this study will further evaluate the safety and efficacy of HMI-115 in pre-menopausal women with endometriosis related pain.

A detailed description of the chemistry, non-clinical pharmacology and toxicology data for HMI-115 is provided in the most updated version of IB.

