λ_z , $t_{1/2}$	
1. The apparent terminal phase rate-constant (λ_z) will be estimated by linear regression of concentration versus time data presented in a log-linear scale.
 
2. Data are primarily monotonically decreasing in magnitude and are representative of the actual decline in the log concentration-time curve.
 
3. Only those data points that are judged to describe the terminal log-linear decline will be used in the regression.
 
4. A minimum number of three data points in the terminal phase will be used in calculating λ_z with the line of regression starting at any post-C_{max} data point (C_{max} should not be part of the regression slope). Unless otherwise determined by PK Scientist's best knowledge and judgment, if the adjusted correlation coefficient (R^2 adjusted) is <0.8, it will be excluded from the summary tables and statistical analysis of PK parameters, and λ_z and all the λ_z dependent parameters (i.e., $t_{1/2}$) will also be flagged and excluded from summary tables and statistical analysis. The reason for exclusion will be listed/footnoted in parameter listings.
 
5. Unless otherwise determined by PK Scientist's best knowledge and judgment, the interval used to determine λ_z should be equal or greater than 1.5-fold the estimated $t_{1/2}$, and if less than 1.5-fold, λ_z will be flagged in listings. All the derived parameters (i.e., $t_{1/2}$) will also be flagged from listings of PK parameters. The reason for flagging will be listed/footnoted in parameter listings.
 
6. The $t_{1/2}$ will be calculated as follows: $t_{1/2} = \ln 2 / \lambda_z = 0.693 / \lambda_z$
 
7. Data points may be dropped from the linear regression if the PK Scientist considers the reported values to be anomalous. Any data points so designated should remain in the listings with a footnote and be identified in the study report with a rationale for exclusion.

MRT	
MRT is Mean residence time from the time of dosing to the time of the last measurable concentration.
 
For non-infusion models:
 $MRT = \frac{AUMC_{last}}{AUC_{last}}$
CL/F	
Total body clearance for extravascular administration, calculated as follows:
 $CL/F = \frac{dose}{AUC_{0-inf}} \text{ (non-steady state) or } CL/F = \frac{dose}{AUC_{0-tau}}$

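### Half-life, AUC0-inf, %AUCextrap, CL/F and Vz/F are planned after dose 1, but about 14 days of sampling cannot meet the SAP's own lambda-z interval rule, and a failing value is only flagged (minor)

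*SAP*

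**What the plan says.** SAP 1.3.3.2 (PK) lists AUC0-10d, AUC0-inf, %AUCextrap, Cmax, Tmax, lambda-z, t1/2, "MRT, CL/F, and V_z/F following dose 1". It lists t1/2, CL/F and Vz/F again after the last dose, together with accumulation ratios.

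SAP 9.1.2 sets the rules for lambda-z:

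- Number of points: "A minimum number of three data points in the terminal phase will be used in calculating λ_z". The regression starts after Cmax, and Cmax itself "should not be part of the regression slope".
- Fit (rule 4): if adjusted R² "is <0.8, it will be excluded from the summary tables and statistical analysis of PK parameters".
- Interval (rule 5): it "should be equal or greater than 1.5-fold the estimated $t_{1/2}$, and if less than 1.5-fold, λ_z will be flagged in listings".

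Rules 4 and 5 each allow an exception for the PK scientist's judgment. No limit on %AUCextrap is given. Summary statistics are suppressed only when fewer than three individual values exist.

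Protocol Table 1-2 gives the intensive-subset samples after dose 1: 2, 4, 6 and 10 days, then the pre-dose sample at Day 15 ± 3. After the last dose, sampling runs to 98 days. Protocol 2.2 reports "peak plasma concentration approximately 4 to 11 days after administration" and an accumulation index of about 2.

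**The concern.** The protocol describes the half-life as long (section 4.2), and the drug peaks late in the two-week dosing interval. The dose-1 profile therefore ends soon after the peak, when dose 2 is given. A terminal slope from such a profile rests on few points over a fraction of one half-life. AUC0-inf, %AUCextrap, t1/2, CL/F and Vz/F all inherit that slope. The SAP's interval rule recognises the problem but does not keep failing values out of the tables. At stake are dose-1 clearance, volume and half-life tables in the study report that look like ordinary estimates but mostly reflect extrapolation.

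**Working it through.** The plan states no half-life, so there is no figure to reproduce. One is derived below and set against what the schedule can support.

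**1. Longest half-life that passes the interval rule after dose 1.** Limit = (last sample − first post-Cmax sample) / 1.5.

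| Cmax at | Points left (days) | Span | Longest t1/2 |
|---|---|---|---|
| day 2 | 4, 6, 10, 14 | 10 d | 6.7 d |
| day 2, visit +3 d | 4, 6, 10, 17 | 13 d | 8.7 d |
| day 4 | 6, 10, 14 | 8 d | 5.3 d |
| day 4, visit +3 d | 6, 10, 17 | 11 d | 7.3 d |
| day 6 | 10, 14 | – | two points, not calculable |
| day 10 | 14 | – | one point, not calculable |

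Day 2 lies below the reported Tmax range of about 4 to 11 days, so 8.7 d is a generous ceiling.

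**2. Half-life implied by the documents.** With rapid absorption and linear PK, steady-state accumulation on a 14-day interval is R = 1/(1 − 2^(−14/t1/2)).

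- Accumulation index of 2 (Protocol 2.2), read as steady state: 14 d. Read as the value after three Q2W doses (1 + q + q² = 2, q = 0.618): 20.2 d.
- Five half-lives covered by Week 25 (Protocol 4.4), 98 days after the last dose: 98/5 = 19.6 d at most.
- Simulated 240 mg figures (Protocol Tables 4-1 and 4-2): AUC 11008/3475 = 3.17 gives 25.6 d; Cmax 36.6/12.4 = 2.95 gives 23.5 d; Ctrough 27.3/9.76 = 2.80 gives 21.9 d.

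The range is about 14 to 26 d. The rule would then need an interval of 1.5 × 14 = 21 d up to 1.5 × 25.6 = 38 d. In the other direction, a t1/2 of 5.3 d would give R of about 1.2, not 2.

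**3. Extrapolated share of AUC0-inf.** Under linear PK, AUCtau at steady state equals single-dose AUC0-inf, so the share beyond day 14 is 1 − 1/R. For R = 2 this is 50%. For the simulated 240 mg dose it is 1 − 3475/11008 = 68%.

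**4. What would reach the tables.** A one-compartment simulation used assumed inputs: t1/2 14 to 25.6 d, absorption rate 0.25 or 0.5 per day, 30% between-subject variability and 5 to 15% residual error. Lambda-z was calculable in about 1 to 44% of subjects and passed the R² rule in about 0.5 to 36%. Under 1% of those that passed also met the interval rule. Median extrapolation was 51 to 77%.

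**5. After the last dose.** From +6 or +14 days to +98 days the span is 92 or 84 days, which passes the rule for t1/2 up to 92/1.5 = 61 d or 84/1.5 = 56 d.

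**The case against.** **The SAP's other rules may leave little to summarise.** This stands in part. A peak at day 6 or later gives no lambda-z, and tables need three values. With 10 subjects per arm and a pass rate of 0.5 to 36%, the chance of three or more values runs from about 0% to 76% (binomial). So it is not certain that such tables will appear. Where they do, they describe the few subjects with an early peak.

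**The PK scientist can exclude values, and %AUCextrap will be visible.** True, but judgment without a criterion is not a planned exclusion, and showing a large extrapolated share does not remove the dependent CL/F and Vz/F.

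**The half-life is derived, not stated.** The accumulation formula assumes absorption is short relative to 14 days, which a Tmax of 4 to 11 days strains. With first-order absorption at rate ka, the share of AUC beyond day 14 is (ka·e^(−14k) − k·e^(−14ka))/(ka − k). Setting this to 50% gives t1/2 of 9.6 d at ka = 0.25 per day and 11.9 d at ka = 0.5 per day. Both still exceed 8.7 d. PK is also more than dose-proportional, so 60 mg may differ from 240 mg, although the repeat-dose regimens in the first-in-human study were 30 to 90 mg.

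**Stronger readings that the documents do not support:**

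- *The estimates are biased towards a short half-life and high clearance.* Ongoing absorption flattens the slope, while selection on R² steepens it. In the simulation, the median estimated t1/2 was 16.5 d against a median true value of 10.8 d in one setting, and 19.7 d against 22.2 d in another. No consistent direction is shown.
- *MRT fails on the same ground.* SAP 9.1.2 defines it as AUMClast/AUClast, which uses no lambda-z.
- *The SAP departs from the protocol without saying so.* Protocol 9.4.9 ties its parameter list to the last dose, and SAP section 10 lists no PK change. But the SAP is based on protocol version 6.1, and the version at hand is 6.0.

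**Conclusion.** The point holds as a minor one. On any half-life that the documents' accumulation figures support (about 14 to 26 d, or about 10 to 12 d at the low end if absorption is slow), the dose-1 profile cannot meet the 1.5-fold rule, whose ceiling is 5.3 d with Cmax at day 4 and 8.7 d at best. About 50% to 68% of AUC0-inf would be extrapolated under linear PK; the 68% belongs to the simulated 240 mg dose only. Because rule 5 flags without excluding, unreliable values can enter the summary tables. Cmax, Tmax, AUC0-10d and the Cmax accumulation ratio are unaffected. The endpoints are exploratory, and no primary or secondary analysis depends on them.

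**What to change.** In SAP 1.3.3.2 and 9.1.2, choose one of these for lambda-z, t1/2, AUC0-inf, %AUCextrap, CL/F and Vz/F after dose 1:

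1. remove them from the dose-1 summaries;
2. list them by subject without summarising; or
3. extend the rule 4 exclusion to values that fail the rule 5 interval criterion.

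Report t1/2, CL/F and Vz/F from the last-dose profile, as already planned. Keep Cmax, Tmax and AUC0-10d after dose 1. Add first-dose AUC0-tau: the AUC accumulation ratio in 9.1.2 needs it, but 1.3.3.2 lists only AUC0-10d, and the derivation table describes AUC0-tau for the last dose only. State how it is handled when the Day 15 visit is early, since Day 12 is only 11 days after dosing. MRT may stay if it is labelled as truncated at the last dose-1 sample.

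The cost is SAP wording and a few table shells. No sampling changes.
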